4.5 DURATION OF PARTICIPATION

The study consists of two periods: a 5-day treatment period (mandatory visits on Days 1, 2, and 4) and a 24-day follow-up period (mandatory visits on Days 6, 10, and 29). Therefore, the total study duration for each participant will be 29 days.

5. STUDY POPULATION

Approximately 100 Chinese pediatric participants aged 1 to < 12 years with influenza symptoms are planned for enrollment in this study. Pharmacokinetic (PK) samples will be collected for baloxavir marboxil treated pediatric participants according to the schedule of activities *until approximately 48 pediatric participants' samples are collected to ensure at least 40 pediatric participants' samples are available for analysis.*

Prospective approval of protocol deviations to recruitment and enrollment criteria, also known as protocol waivers or exemptions, is not permitted.

5.1 INCLUSION CRITERIA

Potential participants are eligible to be included in the study only if all of the following criteria apply:

- Signed Informed Consent Form (ICF)
A parent or authorized adult will be required to sign the ICF on behalf of the pediatric participant. The informed consent/assent of voluntary participation should be obtained in accordance with local requirements.
- Signed Assent Form when appropriate, as determined by participants' age and individual site and country standards
- Age 1 to <12 years at the time of signing ICF
- A participant who has a diagnosis of influenza virus infection and meets all the following conditions.
 - Fever $\geq 38^{\circ}\text{C}$ (tympanic temperature) at screening
AND
 - At least one of the respiratory symptoms of influenza virus infection (e.g., cough and nasal discharge/nasal congestion)
AND
 - A rapid influenza diagnostic test (RIDT) or polymerase chain reaction (PCR) shows positive for influenza A/B, e.g., point-of-care/local laboratory results with use of nasal aspirate, throat swab, or nasal drip/droplet (or other appropriate sample)
Results from local testing as part of standard of care are acceptable if samples are collected within 24 hours of screening and recorded in the participants' medical records.
- The time interval between the onset of symptoms and screening is ≤ 48 hours (the onset of symptoms is defined as the time when body temperature first exceeded 37.5°C if known, or the time when the first symptom was noticed by participant, parent, or caregiver)
- A participant who will be able to take baloxavir marboxil [REDACTED] for oral suspension or oseltamivir capsule for oral suspension/oral in the opinion of the investigator/sub-investigator
- A participant whose parent/guardian is willing and able to adhere to the study requirements in the opinion of the investigator/sub-investigator
- A participant who is able to adhere to the study requirements appropriately for the level of understanding

- PCR (–) or antigen test (–) for severe acute respiratory virus-coronavirus 2 (SARS-CoV-2) *using* point-of-care/local laboratory *test* with nasal aspirate, throat swab, or nasal drip/droplet (or other appropriate sample)

Results from local testing as part of standard of care are acceptable if samples are collected within 24 hours of screening and recorded in the participants' medical records.

5.2 EXCLUSION CRITERIA

Potential participants are excluded from the study if any of the following criteria apply.

- A participant having severe influenza virus infection symptoms requiring inpatient treatment
- *Evidence of* severe renal impairment (equivalent to CLCr < 30 mL/min or estimated glomerular filtration rate < 30 mL/min/1.73 m²), vascular, neurologic, or metabolic disease (e.g., diabetes, thyroid disorders, adrenal disease), uncontrolled hepatitis, cirrhosis, or pulmonary disease (e.g. uncontrolled bronchial asthma)
- Received systemic corticosteroid or immunosuppressive therapy
- Primary immunodeficiency syndrome
- History of organ transplantation
- HIV infection
- Immunization with a live/attenuated influenza vaccine in 2 weeks prior to randomization
- Previous malignancy within the last 5 years or has an active cancer at any site
- Previous encephalitis/encephalopathy, uncontrolled epilepsy with antiepileptic drugs, or influenza virus infection-associated abnormal behavior within the last 2 years
- Complications by an infection requiring systemic antibiotic drug, antifungal and/or antiviral drug at screening
- Use of prohibited concomitant drugs while in the study in the opinion of the investigator
- A participant who received any medications with anti-flu effect such as baloxavir, peramivir, oseltamivir, zanamivir, favipiravir, arbidol, amantadine or traditional Chinese anti-influenza medicines within 30 days before screening
- Known allergy and/or clinically problematic intolerance to baloxavir, oseltamivir and/or acetaminophen
- Diagnosed with or suspected SARS-CoV-2 infection, or close contacts of diagnosed or suspected SARS-CoV-2 infected participants
- Severe underlying disease or condition potentially affecting study evaluation in the opinion of the investigator/sub-investigator
- A participant who received an investigational or unapproved drug product within 30 days or 5 × the half-life before screening, whichever is longer

- Females participants who have commenced menarche (i.e., child-bearing potential)

5.3 LIFESTYLE CONSIDERATIONS

5.3.1 Meals and Dietary Restrictions

This study has no meal or dietary restrictions.

Baloxavir marboxil co-administration with dairy products, calcium-fortified beverages, polyvalent cation-containing laxatives, antacids, or oral supplements (e.g., calcium, iron, magnesium, selenium, or zinc) should be avoided. Therefore, study medication should not be co-administered with any of the aforementioned foods, liquids, or medications.

5.3.2 Caffeine, Alcohol, and Tobacco

This study has no caffeine, alcohol, or tobacco restrictions.

5.3.3 Activity

This study has no activity restrictions.

5.3.4 Contraception Requirements

This study has no contraception requirements.

5.4 SCREEN FAILURES

Individuals who do not meet the criteria for participation in this study (screen failure) cannot be re-screened for the same illness episode, as the time from flu symptom onset to treatment window is limited to 48 hours. The investigator will maintain a record of reasons for screen failure (see Section 8).

6. STUDY TREATMENT, OTHER TREATMENTS RELEVANT TO THE STUDY DESIGN, AND CONCOMITANT THERAPY

The investigational medicinal product (IMP) for this study is baloxavir marboxil. Oseltamivir (also an IMP) will be administered as an active control.

6.1 STUDY TREATMENT ADMINISTERED

Table 5 provides a description of assigned study treatments for this study.

Table 5 Study Treatment Description

| | Baloxavir marboxil | Oseltamivir |
|-----------------------|-------------------------------------|--------------------------------|
| Use | Experimental | Active comparator |
| Drug form | ██████ for oral suspension | Capsules/oral suspension |
| Unit dose strength(s) | 2 mg/mL | 75 mg/capsule |
| Dosage level(s) | 2 mg/kg, 40 mg or 80 mg single dose | 30 mg, 45 mg, 60 mg, 75 mg BID |
| Formulation(s) | Refer to Pharmacy Manual | Refer to Pharmacy Manual |

| | | |
|-------------------------|------------------------|---|
| Packaging | 50-mL glass bottle | Blister packs containing 10 capsules, 1 packs per box |
| Labeling | Per local requirements | Per local requirements |
| Route of administration | Oral suspension | Oral/oral suspension |
| Source | Sponsor | Sponsor |

The treatment regimens are summarized in Section 4.1.

Guidelines for treatment interruption or discontinuation for participants who experience adverse events are provided in Appendix 3.

6.1.1 **Baloxavir marboxil**

Baloxavir marboxil will be supplied by the Sponsor as white to light yellow [REDACTED] for oral suspension in 50-mL glass bottles. Baloxavir marboxil will be administered orally as a single dose on Day 1, only. The [REDACTED] for oral suspension will be reconstituted with water to provide a fixed dose based on the body weight of the child (2 mg/kg for participants weighing <20 kg, or 40 mg for participants weighing ≥20 kg to <80 kg, and 80 mg for those weighing ≥80 kg). For information on the formulation, packaging, and handling of baloxavir marboxil, see the pharmacy manual (see Table 5).

Table 6 Baloxavir Marboxil Administration by Treatment Group

| Participant's Body Weight at Screening | Dose, Formulation |
|--|--------------------------------|
| < 20 kg | 2 mg/kg, oral suspension |
| ≥ 20 kg to < 80 kg | 40 mg (20 mL), oral suspension |
| ≥ 80 kg | 80 mg (40 mL), oral suspension |

6.1.2 **Oseltamivir**

Oseltamivir will be supplied by the Sponsor as a capsule/oral suspension and administered orally BID (morning and evening) for 5 days. Participants can take the capsule directly. If participants can't take the capsule, they can take the oral suspension prepared by the capsule. The powder for suspension will be reconstituted with water, to provide a fixed dose based on the body weight of the child. The first does of oseltamivir will be administered on Day 1 at the site by the investigator/study nurse and the investigator/study nurse will give training on the oseltamivir administration to the parents/guardians. Participants can take the oseltamivir on the second dose on Day 1 and Day 2 to Day 5 at home.

Oseltamivir will be given orally 12 hours apart. If the first dose is taken after 4 p.m. (16:00 hours) on Day 1, the next dose will be taken in the morning of Day 2. For these participants, the tenth dose will be taken on the morning of Day 6. If the first dose is taken prior to 4 p.m. (16:00 hours) on Day 1, the next dose should be taken in the evening of the same day (i.e., prior to midnight on the same calendar day with a minimum of 7 hours between doses). For these participants, the tenth dose will be taken in the evening of Day 5.

For information on the formulation and handling of oseltamivir, see the pharmacy manual and the local prescribing information for oseltamivir (see [Table 7](#)).

Table 7 Oseltamivir Administration by Treatment Group

| Participant's Body Weight at Screening | Dose. Formulation |
|--|---------------------------------|
| ≤ 15 kg | 30 mg BID, oral suspension |
| > 15 kg to ≤ 23 kg | 45 mg BID, oral suspension |
| > 23 kg to ≤ 40 kg | 60 mg BID, oral suspension |
| > 40 kg | 75 mg BID, oral/oral suspension |

BID = twice a day.

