6.7 TREATMENT OF OVERDOSE

An overdose is the administration of a drug in a quantity that is higher than the assigned dose. There is no known antidote for treating an overdose. Cases of overdose, along with any associated adverse events, should be reported as described in [Appendix 3](#).

In the event of an overdose, the investigator should take the following steps:

1. Contact the Medical Monitor immediately.
2. Closely monitor the participant for any adverse event or serious adverse event and laboratory abnormalities for a period per the investigator's judgement.
3. Obtain a plasma sample for PK analysis within 1 day from the date of the last dose of study treatment if requested by the Medical Monitor (determined on a case-by-case basis).

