### **4.4 OTHER SAFETY ANALYSES**

#### **4.4.1 Extent of Exposure**

The duration of treatment exposure will be summarized with descriptive statistics by treatment group for SAS.

The duration of treatment exposure [days] in the oseltamivir group is defined as the dosing period during which a patient takes medication as follows:

$$(\text{final dose date}) - (\text{initial dose date}) + 1$$

For the baloxavir marboxil group, duration of exposure is defined as 1 day if actual baloxavir marboxil [REDACTED] for oral suspension are dosed.

The treatment compliance rate will be summarized with descriptive statistics by the treatment group for the SAS. In addition, the frequency and percentage of patients with compliance <80% and ≥80% will be presented.

The treatment compliance rate [%] in the oseltamivir group is defined as: actual frequency of treatment exposure / expected frequency of treatment exposure \* 100.

For baloxavir marboxil group treatment compliance is defined as 100% if patients are dosed per protocol.

The total dose in milligram will be summarized with descriptive statistics by the treatment group for the SAS.

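### Protocol 6.1.2 lets the 75 mg oseltamivir capsule be taken whole with no weight condition, while Table 7 lists only suspension at 30 to 60 mg up to 40 kg; the two conflict, and the SAP compliance rate would not show which was followed.

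*Protocol*

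**What the plan says.** **Who may take the capsule.** Protocol 6.1.2 states: "Participants can take the capsule directly." A child who cannot do so is offered a suspension made from the capsule. Ability to take the capsule is the only test. The inclusion criterion in 5.1 on being able to take study drug adds no weight condition.

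**What is supplied.** The strength row of Table 5 reads "Unit dose strength(s) | 2 mg/mL | 75 mg/capsule", with baloxavir first and oseltamivir second. The oseltamivir packaging is "Blister packs containing 10 capsules, 1 packs per box". No other oseltamivir strength or pack is listed, although the same table gives dosage levels of 30, 45, 60 and 75 mg.

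**What is assigned.** Table 7, in the same section as the capsule sentence, sets dose and presentation by weight. The three bands up to 40 kg are suspension only; the entry for children over 23 and up to 40 kg, for example, is "60 mg BID, oral suspension". The oral route appears beside suspension only above 40 kg, at 75 mg.

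**Preparation.** 6.1.2 also says: "The powder for suspension will be reconstituted with water, to provide a fixed dose based on the body weight of the child." Table 5 lists no separate oseltamivir powder.

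**Where doses are taken.** Under 6.1.2 the first of ten doses is given at the site, and the rest can be taken at home.

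**How exposure is analysed.** SAP 4.4.1 defines oseltamivir compliance as "actual frequency of treatment exposure / expected frequency of treatment exposure", times 100. The same section also summarises total milligrams by treatment group in the safety set.

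**Overdose.** Protocol 6.7 states: "An overdose is the administration of a drug in a quantity that is higher than the assigned dose."

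**The concern.** Two statements in one section give different answers for the same child. A child of 25 kg who can swallow capsules falls in the 60 mg suspension band of Table 7, yet the sentence above that table allows a 75 mg capsule.

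This matters for three reasons:

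- Oseltamivir is the comparator for the primary objective, which is safety. The planned arm is 33 children, so each child is 1/33 = 3.0 percentage points of it.
- Sites could record the same act differently. Section A3-7.11.1 of Appendix 3 has overdoses and medication errors entered on the Adverse Event eCRF even when no adverse event follows. A site working from Table 7 would enter a whole capsule at 25 kg as an overdose. A site working from the capsule sentence would see nothing to enter.
- The measure a reader would look to first, the compliance rate, contains no milligram term, so it cannot tell the two situations apart.

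**Working it through.** The plan states no figure on this point, so there is none to reproduce. The check is direct arithmetic on its inputs.

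**Inputs**
- Listed unit: 75 mg per capsule (Protocol Table 5).
- Assigned dose D by weight: 30, 45, 60 or 75 mg (Protocol Table 7).
- Course: ten doses, the first at the site (Protocol 6.1.2).
- Compliance: doses taken / doses expected x 100 (SAP 4.4.1).

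**Formulas**, if one whole capsule is taken at each of ten doses:
- dose ratio = 75 / D
- course totals = 10 x 75 = 750 mg taken, against 10 x D assigned
- SAP compliance = 10 / 10 x 100
- milligram ratio = 750 / (10 x D) x 100

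| Weight | Table 7 dose (mg) | Table 7 presentation | 75 / D | Taken vs assigned (mg) | SAP compliance | Milligram ratio |
|---|---|---|---|---|---|---|
| up to 15 kg | 30 | suspension | 2.50 | 750 vs 300 | 100% | 250% |
| over 15 to 23 kg | 45 | suspension | 1.67 | 750 vs 450 | 100% | 167% |
| over 23 to 40 kg | 60 | suspension | 1.25 | 750 vs 600 | 100% | 125% |
| over 40 kg | 75 | oral or suspension | 1.00 | 750 vs 750 | 100% | 100% |

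The conflict is confined to the first three rows. The compliance rate is the same in all four.

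**Would the milligram summary show it?** A total of 750 mg is legitimate above 40 kg. A by-arm summary pools the weight bands, so a 750 mg total in a child assigned 300, 450 or 600 mg need not stand out. SAP 4.5.4 adds exposure by age group, which might prompt a query, but it too is not set against each child's assigned dose.

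**Home doses.** 10 - 1 = 9 doses can be taken at home. The diary described in Protocol 4.1 covers temperature, symptoms and acetaminophen, not oseltamivir doses. What was taken at home therefore reaches the data through the drug administration eCRF (6.4) and returned packaging (6.2).

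**The case against.** The strongest reply is that Table 7 sits directly below the sentence, fixes both dose and presentation for each band, and can be read as limiting a general permission. Several sections say that the oseltamivir dose is based on body weight, and 6.5 forbids modifying it. Nothing instructs a site to give 75 mg to a child of 40 kg or less.

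There are also safeguards. Site staff give the first dose and train the caregiver (6.1.2). Sites must see that children receive the doses the protocol specifies, and must account for drug used (6.2). Dose and timing go on the eCRF (6.4), and overdoses and medication errors are reportable. Preparation is referred to a pharmacy manual that is not among the documents and may settle the matter.

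Much of this stands. It shows that the event is avoidable and that dosing data exist. It does not remove the conflict: the sentence makes suspension the fallback, while Table 7 makes it the only presentation up to 40 kg. A duty to follow the protocol's doses does not help where the protocol gives two answers.

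Stronger readings are tempting, but the documents do not support them:

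- **That comparator children will be overdosed, or a count of them.** About 2/3 x 33 = 22 oseltamivir children are planned to be 5 to under 12 years old, and a guessed share of capsule-takers would give a number. The documents give neither weights nor the share who can swallow capsules.
- **That baloxavir would look safer as a result.** No relation between oseltamivir dose and adverse events is given, and no hypothesis is tested.
- **That milligrams are not analysed at all.** SAP 4.4.1 and Protocol 9.3.2 both plan a total-dose summary.
- **That a powder product is missing from Table 5.** The sentence before it describes suspension made from the capsule, so capsule contents are a natural reading.

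**Conclusion.** The conflict is real. For any child of 40 kg or less who can swallow a capsule, the capsule sentence in 6.1.2 and Table 7 do not agree. Following the sentence with the one listed unit gives 1.25 to 2.50 times the Table 7 dose, and the SAP compliance rate would still read 100%.

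The ratios assume one whole 75 mg capsule per dose for all ten doses. The 2.50 figure applies only at 15 kg or less. This is a statement about what the wording permits. It is not evidence that any child received the wrong amount, nor a finding about the direction of the safety comparison. The only bound available on the number affected is the set of oseltamivir children weighing 40 kg or less, out of 33 planned. Whether the pharmacy manual already resolves the conflict cannot be judged from the documents.

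**What to change.** **Protocol.** The sponsor should reconcile the capsule sentence in 6.1.2 with Tables 5 and 7, so that dose and permitted presentation or presentations agree for each weight band. The text should also say whether the powder means capsule contents. Caregiver instructions should then be brought into line. Which passage governs is for the sponsor to decide.

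**SAP 4.4.1.** Keep the dose count. Beside it, report for each oseltamivir participant the milligrams taken relative to the milligrams assigned under the reconciled protocol, and list every discrepancy. The data source is the dose information that Protocol 6.4 already asks for on the Study Drug Administration eCRF; the check is only as good as the recording of home doses there. If children have already been dosed, this listing is still worth producing.

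**Cost.** A wording change in one protocol section, with whatever ethics review Section A1-1 of Appendix 1 requires; a matching caregiver instruction; one derived variable; and one listing. No added visits, participants or data fields, provided the eCRF holds the amount taken per dose.

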6.1.3 Rescue Medication

If influenza symptoms, such as fever and headache, are so severe, in the opinion of the participant/caregiver, that the participant needs rescue therapy between Days 1 and 29, the use of acetaminophen at a dose appropriate to the age and weight of the child will be permitted. If acetaminophen is used, the participant/parent/caregiver will record the use in the participant diary, and the investigator will record the date, time, and dose at the next visit.

Acetaminophen will not be provided by the Sponsor.

6.2 PREPARATION, HANDLING, STORAGE, AND ACCOUNTABILITY

All IMPs required for completion of this study will be provided by the Sponsor. The study site (i.e., investigator or other authorized personnel e.g., pharmacist or mobile nurse) is responsible for maintaining records of IMP delivery to the site, IMP inventory at the site, IMP use by each participant, and disposition or return of unused IMP, thus enabling reconciliation of all IMP received, and for ensuring that participants are provided with doses specified by the protocol.

The study site should follow all instructions included with each shipment of IMP. The study site will acknowledge receipt of IMPs supplied by the Sponsor, with use of an interactive voice or Web-based response system (IxRS) to confirm the shipment condition and content. Any damaged shipments will be replaced. The investigator or designee must confirm that appropriate temperature conditions have been maintained during transit, either by time monitoring (shipment arrival date and time) or temperature monitoring, for all IMPs received and that any discrepancies have been reported and resolved before use of the IMPs. All IMPs must be stored in a secure, environmentally controlled, and monitored (manual or automated) area in accordance with the labeled storage conditions, with access limited to the investigator and authorized staff.

Only participants enrolled in the study may receive IMPs, and only authorized staff may supply or administer IMPs.

Investigational medicinal products will either be disposed of at the study site according to the study site's institutional standard operating procedure or be returned to the Sponsor with the appropriate documentation. The site's method of destroying Sponsor-supplied IMPs must be agreed to by the Sponsor. The site must obtain written authorization from the Sponsor before any Sponsor-supplied IMP is destroyed, and IMP destruction must be documented on the appropriate form.

Accurate records of all IMPs received at, dispensed from, returned to, and disposed of by the study site should be recorded on the drug accountability log. Caregivers will be reminded to return remaining medicine with packaging and/or empty bottles to the study site.

Refer to the pharmacy manual and/or the Baloxavir marboxil Investigator's Brochure or local prescribing information for information on IMP preparation, storage, handling, and accountability.

6.3 TREATMENT ASSIGNMENT

This is a randomized, open-label study. After initial written informed consent has been obtained, all screening procedures and assessments have been completed, and eligibility has been established for a participant, the study site will obtain the participant's identification number and treatment assignment from an IxRS.

Participants will be randomly assigned in a 2:1 ratio to one of the two treatment arms: a single oral dose of baloxavir marboxil or oseltamivir. *Randomization will be stratified by age group (1–<5 years old versus 5–<12 years old) and high risk factors for influenza complications (with versus without, see [Appendix 8](#) for the definition of high risk factors).*

